8.3 Potential Benefits of Participation in the DEVICE Trial

The primary benefits of the DEVICE trial will be the indirect benefits to society that would result if one type of laryngoscope is found to prevent complications. Because millions of critically ill adults undergo

emergency tracheal intubation each year, if one of the two approaches were found to prevent serious complications, the findings would immediately improve the care provided to millions of severely ill patients. Compared to the minimal risks of participation in the study, the pursuit of these benefits is reasonable.

8.4 Minimization of Risk

Federal regulations 45 CFR 46.111(a)(1) require that risks to patients are minimized by using procedures which are consistent with sound research design. This trial meets this human subjects protection requirement by incorporating numerous design elements to minimize risk to patients.

Both video laryngoscopy and direct laryngoscopy have been used in clinical practice for years with an established safety profile in the same populations included in the DEVICE trial. To further mitigate risk, we will exclude patients for whom treating clinicians determine that a specific laryngoscope is required or contraindicated for the optimal care of the patient.

The trial protocol includes monitoring of adverse events, robust assessment of clinical outcomes, and an interim analysis by an independent DSMB, empowered to stop the trial or modify the trial protocol at any time.

Finally, to limit the risks associated with the collection of protected health information (PHI), the minimum amount of PHI necessary for study conduct will be collected. The data will be coded and stored in a secure online database (REDCap) only accessible by the investigators. REDCap tools will be used to ensure that the PHI that is collected is only visible to investigators at the healthcare system where the patient is enrolled. To protect participant privacy, REDCap tools will be used to ensure that only deidentified data can be exported for use during analysis.

9 Statistical Considerations

9.1 General Considerations

We will present summary tabulations by treatment group. For categorical variables, the number and proportion of patients within each category (with a category for missing data as needed) of the parameter will be presented. For continuous variables, the number of patients, mean or median as appropriate, and standard deviation or interquartile range as appropriate, will be presented.

We will analyze a single pre-specified primary outcome and a single pre-specified secondary outcome using a chi-square test. Consistent with recommendations of the Food and Drug Administration²⁶ and the European Medicines Agency,²⁷ each will be tested using a two-sided P value with a significance level of 0.05. For all other analyses except safety analyses, emphasis will be placed on the estimate of effect size with 95% confidence intervals, as recommended by the *International Committee of Medical Journal Editors*,²⁸ and no corrections for multiple comparisons will be performed.

9.2 Sample Size Estimation

The minimum clinically important difference in successful intubation on the first attempt that would be required to justify routine use of a video laryngoscope rather than a direct laryngoscope in clinical care is uncertain. The current trial will be designed to detect a 5% absolute difference between groups in the incidence of successful intubation on the first attempt. An absolute difference of 5% in successful intubation on the first attempt to or smaller than the difference considered to be clinically meaningful in the design of prior airway management trials.^{8,11,24} Assuming an incidence of successful intubation on the first laryngoscopy attempt of 80% in the direct laryngoscope group based on data from a recently completed trial in the same ED and ICU settings, detecting a 5% absolute increase in the incidence of successful intubation on the first attempt with 90% power at a two-sided alpha level of 0.05 would require enrollment of 1,920 patients (960 per group), anticipating 16 enrolling sites (clusters) and an intra-cluster correlation of 0.05. Anticipating missing data for up to 4% of patients, we will plan to enroll a total of 2,000 patients (1,000 per group).

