9.4.4 Handling of Missing Data

We anticipate that no data on the primary outcome will be missing. When data are missing for the secondary or exploratory outcomes, we will perform complete-case analysis, excluding cases where the data for the analyzed outcome are missing. There will be no imputation of missing data for these outcomes. In adjusted analyses, missing data for covariates will be imputed using multiple imputations.

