The minimum clinically important difference in successful intubation on the first attempt that would be needed to justify routine use of a video laryngoscope rather than a direct laryngoscope in the ED and ICU is uncertain. The current trial is designed to detect a 5% absolute difference between groups in the incidence of successful intubation on the first attempt. An absolute difference of 5% in successful intubation on the first attempt is similar to or smaller than the difference used in the design of prior airway management trials and is considered by airway management experts to be clinically meaningful. 21,28,38,39 Assuming (1) an incidence of successful intubation on the first attempt of 80% in the direct laryngoscope group, (2) 90% statistical power, (3) a two-sided alpha of 0.05, and (4) enrollment at 16 sites with an intra-cluster correlation for the primary outcome of 0.05, we calculated that detecting a 5% absolute increase in the incidence of successful intubation on the first attempt would require enrollment of 1,920 patients (960 per group). Anticipating missing data for up to 4% of enrolled patients, we will plan to enroll a total of 2,000 patients (1,000 per group).

Data and Safety Monitoring Board (DSMB) and Interim Analysis

A DSMB composed of experts with backgrounds in emergency medicine, pulmonary and critical care medicine, anesthesiology, bioethics, and biostatistics has overseen the design of the trial and is monitoring its conduct. The DSMB will review a single interim analysis prepared by the study biostatistician at the anticipated halfway point of the trial, after enrollment of 1,000 patients. The stopping boundary for efficacy was pre-specified as a P-value of 0.001 or less, using a chi-square test, for the difference in the incidence of the primary outcome between groups. This conservative Haybittle—Peto boundary was selected to allow the final analysis to be performed using an unchanged level of significance (P < 0.05). The DSMB retains the authority to stop the trial at any point, request additional data or interim analyses, or request modifications of the study protocol to protect patient safety. Trial safety monitoring and handling of adverse

events are described in detail in the supplementary file, section 5. Patient privacy and data storage details are listed in the supplementary file, section 6.

Statistical Analysis Principles

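### 960 patients per group give about 82–84% power for 80% versus 85%, not the stated 90%

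*Protocol*

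**What the plan says.** Protocol 9.2 gives every input. The control rate is stated as "Assuming an incidence of successful intubation on the first laryngoscopy attempt of 80% in the direct laryngoscope group", and the aim is "detecting a 5% absolute increase in the incidence of successful intubation on the first attempt", that is, 80% versus 85%. The calculation is described as "anticipating 16 enrolling sites (clusters) and an intra-cluster correlation of 0.05". Its result is that this, "with 90% power at a two-sided alpha level of 0.05 would require enrollment of 1,920 patients (960 per group"). The last step reads "Anticipating missing data for up to 4% of patients, we will plan to enroll a total of 2,000 patients (1,000 per group").

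The sample size section of the SAP uses the same inputs, lists as its fourth assumption "4) enrollment at 16 sites with an intra-cluster correlation for the primary outcome of 0.05", and concludes that detection "would require enrollment of 1,920 patients (960 per group"). Neither document gives the formula or software, or says how the ICC entered.

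Three other provisions bear on the check. Protocol 5.3 randomises individual patients 1:1, stratified by site. Protocol 9.1 and 9.4.1 and the SAP's main analysis specify a two-sided 0.05 chi-square test without adjustment for site. Protocol 9.4.4 adds "We anticipate that no data on the primary outcome will be missing".

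**The concern.** For 80% versus 85% at two-sided 0.05, 960 per group falls between the sizes for 80% and 85% power. The ICC is the only stated input that could move the number, and 0.05 is too small to move it that far.

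The power claim supports how a null result will be read. The Protocol background and the SAP introduction justify this trial because earlier ones were too small to exclude clinically important differences. If this trial is null, readers will assume a 10% type II error at 5 points, when it is about 16–18% at the planned evaluable size.

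Protocol 9.4.5 also lets the DSMB suggest sample size re-estimation if the control rate departs substantially from 80%. If the stated calculation were the baseline, a correct recalculation would ask for some 2,300–2,420 evaluable patients even at exactly 80%. That increase could be mistaken for one driven by the interim data.

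**Working it through.** **Inputs** (Protocol 9.2 and SAP): p1 = 0.80, p2 = 0.85, mean 0.825, difference 0.05, two-sided alpha 0.05 (z = 1.960), power 90% (z = 1.2816), 1:1 allocation, 16 sites, ICC 0.05.

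**1. Trying to reproduce 960.** The pooled two-proportion formula is

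n per group = [z_α √(2 × 0.825 × 0.175) + z_β √(0.80 × 0.20 + 0.85 × 0.15)]² / 0.05²

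= [1.960 × 0.53735 + 1.2816 × 0.53619]² / 0.0025 = 1.7404² / 0.0025 = 1,211.5, so 1,212 per group and 2,424 in total.

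Variants do not help: unpooled variance gives 1,209, the arcsine method 1,208 and the continuity correction 1,252. The pooled formula gives 906 per group for 80% power and 1,036 for 85%.

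**2. Effect of the ICC.**
- *Patients randomised within sites (the actual design).* Between-site variation cancels from the comparison, so the variance factor is at best 1 − 0.05 = 0.95. Then 1,211.5 × 0.95 = 1,151 per group, 2,302 in total.
- *ICC needed to reach 960.* 960 / 1,211.5 = 0.79, an ICC of about 0.21, together with a site-stratified test.
- *Sites as randomised units (not this design).* With 1,920 / 16 = 120 patients per site the design effect is 1 + 119 × 0.05 = 6.95, giving 1,211.5 × 6.95 ≈ 8,420 per group. This shows direction only: read this way, the ICC raises the number.

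**3. Power at the planned sizes.** For the chi-square test ignoring site, z = (0.05 √n − 1.960 × 0.53735) / 0.53619.
- n = 960: (1.5492 − 1.0532) / 0.53619 = 0.925, power 82.3%.
- n = 1,000: (1.5811 − 1.0532) / 0.53619 = 0.985, power 83.8%.

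With ICC 0.05, the planned chi-square test keeps the larger standard error while the true one shrinks by √0.95. So z becomes 0.925 / 0.9747 = 0.949 and 0.985 / 0.9747 = 1.010. A site-stratified test gains the full factor, equivalent to replacing n by n / 0.95.

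| Analysis | 960 per group | 1,000 per group |
|---|---|---|
| Chi-square, no ICC | 82.3% | 83.8% |
| Chi-square, ICC 0.05 | 82.9% | 84.4% |
| Site-stratified, ICC 0.05 | 84.1% | 85.6% |

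A simulation of 16 sites with 60 patients per arm and beta-distributed site rates gave 82.7% (chi-square) and 83.8% (Cochran–Mantel–Haenszel). A further simulation of that layout gave 82.2% and 83.3%, so these are good to about half a point.

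**4. Difference detectable with 90% power** (control rate 80%): 5.6 points at 960 per group and 5.5 at 1,000 for the chi-square test ignoring site; 5.4 and 5.3 for the stratified test.

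**5. Shortfall in evaluable patients.** Against 1,920: 2,302 − 1,920 = 382 to 2,424 − 1,920 = 504. Against 2,000, if nothing is missing: 302 to 424.

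**6. Missing-data step.** 1,920 / 0.96 = 2,000. This step is correct.

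**The case against.** The best candidate for the origin of the figure is a one-sided alpha of 0.05. That gives 988 per group, or 938 with the 0.95 factor. Neither equals 960, but both are within 3% of it, and one-sided power at 960 would be 89.3–90.6%. This may be the source, though nothing in the documents shows it. It does not rescue the claim, because both documents state a two-sided alpha for design and analysis.

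Second, the trial enrols 2,000 and expects no missing primary outcome data, so 1,000 per group may be the fairer basis. That is reasonable, and both sizes are shown above. Power still falls 4–6 points short of 90%, with a type II error of about 14–16%.

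Third, the stratified figures describe a test that is not the planned primary analysis. This stands: the chi-square figures should lead, with the stratified ones as the most favourable reading.

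Fourth, the consequences are limited. Power stays above 80%, type I error and the estimate are unaffected, and the risk difference will be reported with a 95% confidence interval, which helps a careful reader. Re-estimation is only something the DSMB may suggest, and nothing says that this calculation would be reused. These points reduce the harm, but the stated power is still wrong in both documents.

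**Conclusion.** The concern holds. On the documents' own inputs, 90% power needs 1,212 per group, or 1,151 on the most favourable use of the ICC. No reading of an ICC of 0.05 with a two-sided alpha gives 960. With 960 evaluable per group, power is about 82–83% for the planned test and about 84% for a site-stratified one.

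This rests on the stated 80% and 85%, 1:1 allocation within sites and, for the ICC figures, 16 equal-sized sites. The interim look at P ≤ 0.001 has a negligible effect on power. The correction should be made, because a headline design claim is wrong in both documents.

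**What to change.** Keep the enrolment target of 2,000 and change the claim in Protocol 9.2 and the SAP's sample size section. Suggested content: with 960 evaluable patients per group, the trial has about 83% power by the planned chi-square test (about 84% with a site-stratified test) for 80% versus 85%, and 90% power for a difference of about 5.4–5.6 points. Give the figures for 1,000 per group alongside (about 84% and 85.6%; 5.3–5.5 points), because the plan both allows for 4% missing data and expects no missing primary outcomes.

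State the formula or software used and how the ICC entered. With randomisation within sites it can act only as a (1 − ICC) variance reduction, and the full gain requires an analysis stratified by site. Any interim re-estimation should start from the corrected calculation.

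The cost is wording in two documents and a less favourable stated power. No extra patients are needed, and the test and alpha do not change.

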9.3 Analysis Populations

The primary analysis will occur in an intent-to-treat (ITT) fashion among all patients randomized, excluding only those patients whose data was withdrawn from the study (e.g., a patient who became a prisoner during the follow up period).

9.4 Statistical Analysis

Before enrollment is complete, a complete final statistical analysis plan will be made publicly available. Analyses conducted in accordance with the statistical analysis plan will be identified as *a priori*. Any additional analyses requested by the investigators or reviewers after completion of enrollment will be identified as *post hoc*.

9.4.1 Primary Analysis

Main analysis of the primary outcome. The primary analysis will be an intention-to-treat comparison of patients randomized to the video laryngoscope group versus patients randomized to the direct laryngoscope group with regard to the primary outcome of successful intubation on the first attempt. The difference in proportion and the associated 95% confidence interval will be presented. Between group differences will be examined using a Chi-square test.

9.4.2 Secondary Analyses

We will perform:

- 1. Intention-to-treat comparisons of secondary, exploratory, and safety outcomes; and
- 2. Intention-to-treat comparison of the primary outcome between groups using a generalized linear mixed effects model including a random effect for site and fixed effects for group assignment and pre-specified baseline variables, including: age; sex; body mass index; and location at enrollment (ED or ICU).

9.4.3 Effect Modification (Subgroup Analyses)

To evaluate whether pre-specified baseline variables modify the effect of study group assignment on the primary outcome, we will perform logistic regression modelling with the primary outcome as the dependent variable and independent variables of the study group, the proposed effect modifier, and the interaction between the two. Any interaction term with a p-value less than 0.1 will be considered to identify an effect modifier. To account for non-linear relationships, continuous variables will be analyzed using restricted cubic splines with between 3 and 5 knots. Forest plots will be used to graphically display the adjusted analyses, and locally weighted regression or partial effects plots will be used to portray the association between continuous covariates and the outcome. A full list of prespecified subgroup analyses will be outlined in the detailed Statistical Analysis Plan and will include:

- Operator Experience
 - Total number of previous intubations performed by operator
 - Number of previous intubations performed by operator with a direct laryngoscope
- Operator's planned video laryngoscope (hyperangulated blade vs. non-hyperangulated blade)
- Location (ED vs ICU)
- Presence of difficult airway characteristics
- Indication for tracheal intubation of trauma (Yes vs No)
- Chest compressions being delivered during the first laryngoscopy attempt (Yes vs No)

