At no time during this study, its analysis, or its publication will patient identities be revealed in any manner. The minimum necessary data containing patient or provider identities will be collected. Data collected from the medical record will be entered into the secure online database REDCap. Hard copies of the data collection sheet completed at the time of the airway management event will be stored in a locked room until after the completion of enrollment and data cleaning. Following publication of the study results, all hard copies of data collection forms will be destroyed and the REDCap database will be fully de-identified in accordance with institutional regulations.

11 Follow-up and Record Retention

Patients will be followed after enrollment for up to 28 days or until hospital discharge, whichever occurs first. Data collected from the medical record will be entered into the secure online database REDCap. Hard copies of the data collection sheet completed at the time of the airway management event will be stored in a locked room until after the completion of enrollment and data cleaning. Once data are verified and the database is locked, all hard copies of data collection forms will be destroyed. All data will be maintained in the secure online database REDCap until the time of study publication. The minimal PHI that is collected will be available only to site investigators at the site where the patient was enrolled. At the time of publication, a de-identified version of the database will be generated.

12 Safety Monitoring and Adverse Events

Assuring patient safety is an essential component of this protocol. Use of a video laryngoscope and use of a direct laryngoscope are both standard-of-care interventions that have been used in clinical practice for decades with an established safety profile. However, any trial conducted during a high-risk, time-sensitive procedure like tracheal intubation of critically ill patients raises unique safety considerations. This protocol addresses these considerations through:

- 1. Exclusion criteria designed to prevent enrollment of patients likely to experience adverse events from intubation using a video laryngoscope or intubation using a direct laryngoscope;
- 2. Systematic collection of outcomes relevant to the safety of intubation using a video laryngoscope or intubation using a direct laryngoscope;
- 3. Structured monitoring, assessment, recording, and reporting of adverse events.

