A trained observer, not directly involved with the intubation procedure, collects data for key peri-procedural outcomes. These outcomes include successful intubation on the first attempt, time interval between laryngoscopy and successful intubation, the oxygen saturation and systolic blood pressure at induction, the lowest oxygen saturation and systolic blood pressure between induction and 2 minutes after successful intubation, and new or increased vasopressor administration between induction and 2 minutes after successful intubation.

Observers may be clinical personnel on the enrolling unit (e.g., physician, nurse, or pharmacist) or research study personnel.

Immediately following the intubation procedure, the operator completes a paper data collection form to record the approach to preoxygenation, oxygenation and ventilation between induction and laryngoscopy, the brand of laryngoscope used, the blade shape, the Cormack-Lehane grade of laryngeal view³⁵, use of the video screen to visualize the larynx (if applicable), use of a bougie or a stylet, reasons for failure to intubate on the first attempt (if applicable), intubation approaches on subsequent attempts, difficult airway characteristics observed before

or during the procedure (facial trauma, small mouth opening, limited neck mobility, cervical collar, large neck, obesity, fluids obscuring view of vocal cords, upper airway obstruction or edema), and complications of intubation (witnessed pulmonary aspiration, esophageal intubation, injury to airways, injury to teeth, cardiac arrest between induction and 2 minutes following intubation). Operators record their specialty, training level, and estimates of the number of previous intubations they have performed and the number of previous intubations they have performed using a direct laryngoscope.

Study personnel at each site review the medical record to collect data on baseline patient characteristics, pre- and post-laryngoscopy management, and clinical outcomes at 28 days after enrollment.

The following variables are collected:

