We will examine whether pre-specified baseline variables modify the effect of study group assignment (video laryngoscope vs direct laryngoscope) on the primary outcome using a formal test of statistical interaction in a generalized linear mixed effects model with the primary outcome as the dependent variable, study site as a random effect, and fixed effects of study group, the pre-specified proposed effect modifier, and the interaction between the two. For categorical variables, we will present the odds ratio and 95% confidence intervals within each pre-specified subgroup. Continuous variables will not be dichotomized for analysis of effect modification but may be dichotomized for data presentation. In accordance with the Instrument for assessing the Credibility of Effect Modification Analyses (ICEMAN) recommendations⁴⁴, we have prespecified the following limited number of baseline variables as potential effect modifiers and the hypothesized direction of effect modification for each:

- Patient location (ED vs ICU). We hypothesize that patient location will not modify the effect of study group assignment on the primary outcome.
- 2. Traumatic injury (Yes vs No). We hypothesize that traumatic injury will modify the effect of study group assignment on the primary outcome, with a greater increase in the

- incidence of successful intubation on the first attempt with use of a video laryngoscope compared with a direct laryngoscope among patients with traumatic injury compared to patients without traumatic injury.
- 3. Body mass index (kg/m²). We hypothesize that body mass index will modify the effect of study group assignment on the primary outcome, with a greater increase in the incidence of successful intubation on the first attempt with use of a video laryngoscope compared with a direct laryngoscope among patients with higher body mass index as compared to patients with lower body mass index. This hypothesis of effect modification is supported by a non-significant trend toward effect modification in a meta-analysis of multiple prior randomized trials.⁹

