- 4. Operator's pre-enrollment assessment of the anticipated difficulty of intubation (Easy; Moderate; Difficult; Not Recorded). We hypothesize that the operator's pre-enrollment assessment will modify the effect of study group assignment on the primary outcome, with a greater increase in the incidence of successful intubation on the first attempt with use of a video laryngoscope compared with a direct laryngoscope among patients assessed as Difficult or Moderate compared to Easy. This hypothesis of effect modification is supported by significant effect modification in a meta-analysis of multiple prior randomized trials.⁹
- 5. Operator experience at the time of enrollment.
 - 1. Total number of previous intubations performed by operator. We hypothesize that the total number of previous intubations performed by the operator will modify the effect of study group assignment on the primary outcome, with a greater increase in the incidence of successful intubation on the first attempt with use of a video laryngoscope compared with a direct laryngoscope among operators with fewer previous intubations compared to operators with a greater number of previous intubations. This hypothesis of effect modification is supported by significant

effect modification observed in a prior randomized trial among critically ill adults, but differs from a meta-analysis including trials of intubation in the operating room that did not observe effect modification based on the operator's prior experience. 9,28

2. Proportion of previous intubations performed by the operator using a direct laryngoscope. We hypothesize that the proportion of previous intubations performed by the operator using a direct laryngoscope will modify the effect of study group assignment on the primary outcome, with a greater increase in the incidence of successful intubation on the first attempt with use of a video laryngoscope compared with a direct laryngoscope among operators with a lower proportion of previous intubations performed by the operator using a direct laryngoscope compared to operators with a higher proportion of previous intubations performed by the operator using a direct laryngoscope.

We will also perform an effect modification analysis for the primary outcome that includes a three-way interaction between study group, total number of previous intubations performed by the operator, and proportion of previous intubations performed by the operator using a direct laryngoscope.

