Sensitivity Analyses of the Primary Outcome

We will assess the robustness of the findings of the primary analysis in a number of sensitivity analyses. First, because operators may choose to deviate from the assigned laryngoscope for the safety of the patient, we will repeat the primary analysis, but will consider patients for whom the operator crossed over on the first attempt from the assigned laryngoscope type to the non-assigned laryngoscope type not to have experienced successful intubation on the first attempt. Second, we will repeat the primary analysis among only patients

for whom data on the primary outcome from the independent observer is available (i.e., excluding cases in which operator self-report was the sole source of information for the primary outcome). Third, because the operator's prior experience with each type of laryngoscope may affect the likelihood of success with a video laryngoscope compared with a direct laryngoscope, we will repeat the primary analysis among only cases in which the proportion of prior intubations the operator has performed using a direct laryngoscope is between 0.25 and 0.75.

Analysis of the Secondary Outcome

For the secondary outcome, severe complications occurring between induction and 2 minutes following intubation, we will perform an unadjusted, intention-to-treat comparison of patients randomized to the video laryngoscope group versus patients randomized to the direct laryngoscope group, using a chi-square test.

Analyses of Exploratory Outcomes

For all pre-specified exploratory outcomes, we will conduct unadjusted, intention-to-treat analyses comparing patients randomized to the video laryngoscope group versus patients randomized to the direct laryngoscope group. We will calculate absolute risk differences or differences in medians between groups with the associated 95% confidence intervals.

Handling of Missing Data

We anticipate that no data on the primary outcome will be missing. When data are missing for the secondary or exploratory outcomes, we will perform complete-case analysis, excluding cases where the data for the analyzed outcome are missing. There will be no imputation of missing data for these outcomes. In adjusted analyses, missing data for covariates will be imputed using multiple imputations.

Trial status

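### The operator-experience interactions are tested with no operator term, and no operator code is listed among the data, so their intervals are too narrow if the device effect varies between operators of similar experience.

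*Protocol*

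**What the plan says.** **Model.** Protocol 9.4.3 specifies logistic regression with "independent variables of the study group, the proposed effect modifier, and the interaction between the two". The SAP (Effect Modification) replaces this with a mixed model having "study site as a random effect, and fixed effects of study group, the pre-specified proposed effect modifier, and the interaction between the two". Neither includes an operator effect, an operator-specific device effect or standard errors clustered on operator.

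**Modifiers.** Protocol 9.4.3 lists "Total number of previous intubations performed by operator" and the count done with a direct laryngoscope. The SAP keeps the first, replaces the second with "Proportion of previous intubations performed by the operator using a direct laryngoscope", and adds a "three-way interaction between study group, total number of previous intubations performed by the operator" and that proportion.

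**Operator data.** In the SAP (Data Collection), "Operators record their specialty, training level, and estimates of the number of previous intubations they have performed", together with the number done with a direct laryngoscope. Protocol 7.1 lists training level, specialty and prior experience. Neither list contains an operator code. Protocol section 10 says only that "The minimum necessary data containing patient or provider identities will be collected".

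**Who intubates.** Under the third inclusion criterion (Protocol 3.1), the planned operator must be someone who intubates regularly in that unit.

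**The concern.** Patients are randomised one by one, but experience is a property of the operator. With 2,000 patients in 16 units (SAP, Trial status), each unit supplies 2,000/16 = 125 intubations on average, so many operators will probably contribute several.

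If operators with the same experience differ in how much they gain from video, those differences do not average out over patients, only over operators. They add to the variance of the interaction estimate, and the stated models leave that part out. A random site effect does not supply it, because it shifts the success rate of a whole unit and says nothing about device effects that differ between operators within a unit.

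At stake is the credibility of the answer on operator experience. Protocol section 1 criticises earlier trials for being limited to inexperienced trainees, and the SAP invokes a formal credibility standard for effect modification. A few busy operators who happen to do better with one device could produce an apparent experience effect.

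**Working it through.** **The plan's own figure.** There is none to reproduce. No power, precision, number of operators or operator-level correlation is given for any interaction. Clustering appears in the sample size only by site (16 sites, intra-cluster correlation 0.05).

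**Inputs from the documents.** 1,000 patients per group; success 80% (direct) and 85% (video).

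**Inputs assumed.** Number of operators K from 100 to 800, which is about 6 to 50 per unit (100/16 and 800/16). SD of the device log odds ratio between operators of equal experience, tau, from 0 to 0.8. Experience is standardised to SD 1, with no true interaction.

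**Step 1: variance that the planned model reports.** Ignoring site,

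V0 = 1/(1,000 × 0.80 × 0.20) + 1/(1,000 × 0.85 × 0.15) = 0.00625 + 0.00784 = 0.01409, so SE = 0.119.

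The simulated model SEs, with site indicators in the model, were 0.117 to 0.122.

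**Step 2: variance that it omits.** Operator differences in device effect add about tau² × c, where c = (sum of squared caseloads)/(square of summed caseloads). With equal caseloads c = 1/K; with exponentially distributed caseloads c is about 2/K.

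Check, equal caseloads, K = 100, tau = 1.0: 0.01409 + 1/100 = 0.02409, SD 0.155. The simulated SD was 0.155.

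**Step 3: actual error rate of a nominal 5% test.** With r = √(1 + tau² c/V0), the rejection rate is 2 × [1 − Φ(1.96/r)].

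Example, uneven caseloads, K = 100, tau = 0.5: added variance 0.25 × 2/100 = 0.005; r = √(1 + 0.005/0.01409) = 1.164; 1.96/1.164 = 1.684; rejection 9.2%.

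| Operators | Formula, tau 0.3 | Formula, tau 0.5 | Formula, tau 0.8 | Simulated, tau 0.5 to 0.8 |
|---|---|---|---|---|
| 100 | 6.5% | 9.2% | 15.6% | 9 to 17% |
| 200 | 5.7% | 7.1% | 10.4% | 6 to 11% |
| 400 | 5.4% | 6.0% | 7.7% | about 7% |
| 800 | 5.2% | 5.5% | 6.3% | 5 to 7% |

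The formula columns use uneven caseloads. The simulated column pools runs of 1,000 to 2,000 trials per setting, with and without site indicators, so each rate carries a Monte Carlo error of up to about 1 point.

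**Step 4: is the condition needed?** Yes. When operators differed in general skill but not in device effect (tau = 0), the true SD was 0.95 to 1.05 times the model SE and coverage of the 95% interval was 94 to 96%. At tau = 0.3, simulated rejection was 4.6 to 6.0%.

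**Step 5: does clustering on operator help?** In runs with site indicators and tau up to 1.0, operator-clustered standard errors gave 4 to 8% at the 5% level in every setting. With 100 operators of uneven volume and tau 0.5 to 0.8 they gave 7.5 to 7.8%. They have a cost: with 100 operators and no spread, one run gave 8.3% against 5.3% for the planned model.

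**The case against.** **The documents do not say that operators of equal experience differ.** This stands. The SAP (Sensitivity Analyses) says that "the operator's prior experience with each type of laryngoscope may affect the likelihood of success with a video laryngoscope compared with a direct laryngoscope", and a reader might infer that the plan itself expects the spread at issue. It does not: that sentence concerns prior experience, which is the modifier under test. The spread remains an assumption.

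**The operator may be identifiable after all.** This also stands. A reader might infer from the variable lists that the matter cannot be put right after the trial. Protocol section 10 mentions provider identities and allows records to be reopened until publication to answer data queries, and the SAP's supplementary file is not in the text reviewed. That a code is not listed is established; that none is held is not.

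**The SAP supersedes the protocol's model.** Partly right. Under the SAP, patients are independent given site, so it would be wrong to say that the final model treats all 2,000 as wholly independent. The gap within site remains. The protocol's rule of declaring a modifier at p < 0.1 is not restated in the SAP, so the sizes above use the 5% level.

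**The effect may be small.** Fair. With 800 operators, about 2.5 patients each, inflation is slight even at tau 0.8, and nothing in the documents points to as few as 100 operators.

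**These are secondary analyses.** True. The SAP puts the emphasis on estimates and 95% intervals. But the interval is precisely what is affected.

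**Conclusion.** The concern holds conditionally. Three facts are established: the modifiers are operator-level, neither document's interaction model has an operator term, and no operator code is listed. It follows that the intervals for these interactions are too narrow if the device effect varies between operators of similar experience.

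The amount cannot be fixed from the documents, because both the number of operators and the spread are assumed. It ranges from negligible (spread of 0.3 or less, or many operators with two or three patients each) to a false-positive rate two to three times nominal (100 operators, spread 0.5 to 0.8). The priority is modest. The point is confined to the two operator-experience modifiers and their three-way interaction. A reader might extend it to the main result, but patients are randomised individually and the primary chi-square analysis is unaffected.

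**What to change.** 1. Confirm that a coded operator number is held, or add one to the operator's form with the key kept at the site. This is best settled early, because the paper forms are to be destroyed (after database lock in Protocol section 11, after publication in section 10).
2. Report the number of operators and the distribution of patients per operator.
3. For the two operator-experience modifiers and the three-way interaction only, state in the SAP that inference is clustered on operator, using either cluster-robust standard errors with a small-sample correction or a bootstrap that resamples whole operators.
4. Treat a model with operator random effects (intercept and device slope) as an optional check. It was not simulated here. With 400 operators there are about 2,000/(400 × 2) = 2.5 patients per operator per arm with a binary outcome, so the slope variance may be weakly identified.

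**Cost.** One coded field, a few lines of SAP text and somewhat wider intervals. Error control would still be slightly imperfect if operators are few. The simulations used uncorrected clustered standard errors; the small-sample correction and the bootstrap were not tested. The primary analysis needs no change.
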